Patients who do not fulfill Dosing Criteria ([Section 7.1](#)) may miss up to 2 consecutive doses in Phase 1b or Phase 2 or patients may miss up to 4 total doses in Phase 1b or up to 6 total doses in Phase 2 for any reason (e.g. AE, scheduling, emergency). Upon resumption of dosing, subsequent doses should be timed according to the original dosing schedule based on Day 1. Patients who cannot resume dosing within 2 weeks of the first missed dose or who miss more than 4 total doses in Phase 1b or 6 total doses in Phase 2 must permanently discontinue KZR-616 unless the doses in question were missed based on Study Stopping Rules ([Section 9.1](#)). If doses were missed due to implementation of Study Stopping Rules, then the patient should be discussed with the medical monitor to evaluate if KZR-616 should be discontinued. Any dose modifications should be discussed with the medical monitor and documented in the eCRF.

If study medication is permanently discontinued due to an AE, standard therapy and planned assessments (see Schedule of Assessments, [Section 14.1](#), Appendix A, and [Section 14.2](#), Appendix B, for Phase 1b and Phase 2, respectively) should continue for the protocol specified time period.

7.2 **Prior and Concomitant Medications**

A concomitant medication is any prescription or over-the-counter preparation, including vitamins and supplements. Any concomitant therapies must be recorded on the eCRF. Except as described below, prior and concomitant medication use will be recorded for the 60 days prior to screening until the last follow-up visit.

All prior SLE treatment (e.g., immunosuppressants, antimalarials, biologics) will be recorded, including corticosteroid use, from at least the previous 24 weeks prior to screening. When possible, all prior biologics should be recorded.

SLE Disease-Related Concomitant Medications

Patients should continue all concomitant medications related to SLE therapy throughout the study, as outlined in Inclusion/Exclusion Criteria (Section 5.2), this section (Section 7.2), and Table 3.

- All immunosuppressant therapies and antimalarial agents should be continued at a stable dose except when change is deemed necessary by the treating physician or clinical investigator, or if access is limited due to supply issues (see also Section 7.2.2).

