8.2.6.5 Proteinuria Evaluation

Proteinuria will be assessed via spot UPCR (should be first morning void in all patients with nephritis) and 24-hour urine collection (Phase 1b patients with nephritis and all Phase 2 patients).

Patients should be given specific instructions on the 24-hour urine collection. At a minimum, patients should be instructed to collect urine over a 24-hour period, to keep the sample cold during the collection period and until the sample is returned to the study site, and to return the sample (within 7 days after collection completed for screening).

At screening, patients will be instructed to collect two 24-hour urine collection samples, at least 7 days apart. Both samples must demonstrate UPCR levels meeting protocol inclusion in order to be eligible for Phase 2 study entry. If one of these samples fails to demonstrate UPCR levels meeting protocol inclusion for Phase 2, one additional 24-hour urine collection sample may be obtained at least 7 days from the last sample taken. In addition, a first morning void sample will also be collected at these same time points for a spot UPCR.

Once enrolled into the Phase 2 portion, 24-hour urine samples will be collected at Weeks 1, 5, 9, 13, 17, 21, 25, 29, 33, and 37. Patients should be instructed to return the chilled 24-hour urine sample to the clinic following its collection, which should occur during the 48 hours prior to the visit. A first morning void sample should also be collected at these same time points for a spot UPCR.

The 24-hour urine collection sample will be used to assess UPCR level at the specified visits. If the laboratory test results indicate a urine collection sample is inadequate at any time point, the spot UPCR obtained from the first morning void sample may be used instead for assessments performed at randomization and onward.

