9.2 Early Withdrawal of Patients from Study

Patients may stop study drug for any of the following reasons:

-
- Patient request/withdraw consent due to an AE
 - Patient request/withdraw consent for any reason other than an AE
 - Patient becomes pregnant
 - Use of non-permitted concurrent therapy
 - Non-compliance with the study drug or study schedule
 - AE of \geq Grade 4
 - Lost to follow-up
 - Occurrence of AEs not compatible with the continuation of patient participation in the study, in the investigator's or sponsor's opinion, or unacceptable to the patient to continue
 - Investigator request
 - Sponsor request

For Phase 1b, patients who do not comply with the protocol or who withdraw consent may be replaced. For Phase 2, only patients who withdraw before the Week14 injection may be replaced.

Patients are free to withdraw from the study at any time without providing reason(s) for withdrawal and without prejudice to further treatment. The reason(s) for withdrawal will be documented in the eCRF. If a patient withdraws consent, all samples obtained will be retained for analysis unless the patient confirms that he or she wishes the samples to be discarded.

Patients withdrawing from the study treatment will be encouraged to complete the Early Withdrawal Visit within 7 days and return for an EOS Visit approximately 12 weeks after receipt of their last dose to complete the final evaluations according to this protocol, particularly safety evaluations. The aim is to record data in the same way as for patients who completed the study.

Reasonable efforts will be made to contact patients who are lost to follow-up. These efforts must be documented in the patient's file.

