9.3 Early Withdrawal (or Discontinuation) Visit

The Early Withdrawal Visit will take place within 7 days after withdrawal. The following procedures will be performed at the Early Withdrawal Visit:

- Record any AEs that have occurred since the last visit and any changes in concomitant medication
- Record vital signs
- Record any changes from baseline in physical examination as AEs
- Collect samples for hematology, clinical chemistry, and urinalysis tests

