11.1.2 Phase 2 Endpoints

Primary Endpoint:

- The number of patients with a 50% reduction in UPCR after 24 weeks of treatment when compared to baseline

Secondary Endpoints:

- Safety and tolerability of KZR-616 as assessed by the incidence, nature, and severity of AEs

-
- The number of patients with a partial renal response (PRR) after 24 weeks of treatment as defined by:
 - a) A 50% reduction of UPCR and/or reduction of UPCR to < 1.0 if the baseline UPCR was < 3.0 or a 50% reduction of UPCR and/or reduction of UPCR to < 3.0 if the baseline was ≥ 3.0
 - b) eGFR of ≥ 60 mL/min/1.73 m² or no worsening of eGFR from baseline of $\geq 25\%$
 - c) No use of prohibited medication
 - The number of patients with a complete renal response (CRR) after 24 weeks of treatment as defined by:
 - a) UPCR of ≤ 0.5
 - b) eGFR of ≥ 60 mL/min/1.73 m² or no worsening of eGFR from baseline of $\geq 25\%$
 - c) Prednisone (or equivalent) < 10 mg
 - d) No use of prohibited medication
 - Time to $\geq 50\%$ reduction in UPCR from baseline
 - Time to CRR
 - Time to PRR
 - Time to UPCR of ≤ 0.5 from baseline
 - The number of patients with UPCR of ≤ 0.5 at 24 weeks
 - The number of patients with daily prednisone (or equivalent) dose ≤ 10 mg
 - Change from baseline in levels of autoantibodies (e.g. ANA, anti-dsDNA) and complement at 24 weeks
 - Changes in corticosteroid use from baseline

Exploratory Endpoints:

- The level of proteasome inhibition in whole blood and PBMCs, as measured by both a cleavable fluorogenic substrate enzymatic assay and a subunit-specific proteasome active site ELISA
- Change from baseline in SLEDAI-2K score, CLASI, and 28 joint count and changes from baseline in laboratory measures
- The proteomic and pharmacogenomic activity of KZR-616 will be assessed through ex vivo analysis of whole blood and PBMC samples
- Serum cytokine levels and circulating leukocytes will be measured in blood samples collected on Day 1 of Weeks 1, 5, 17 and 25

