11.3.6 Handling of Missing Data

All withdrawals will be included in all analyses up to the time of withdrawal. Patients who are withdrawn prematurely from investigational product and/or the study will be included in all analyses regardless of the duration of treatment. There will be no imputation for missing data, unless otherwise specified.

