- c If not available from within 90 days prior to signing informed consent form.
- d Vital signs: Systolic and diastolic blood pressure, pulse, and body temperature. Vital signs should be checked after patient has been resting quietly in a supine position for 10 minutes, and should be checked prior to blood draws or study drug administration.
- e ECG done prior to vital signs during supine rest.
- f KZR-616 dose administration on day one of each week from Week 1 up to Week 24. Negative urine pregnancy test required prior to dose administration.
- g Urine biomarkers from 24-hour urine.
- h ANA, anti-dsDNA, anti-Sm, anti-RNP, anti-Ro/La (anti-SSA/SSB), C3/C4, and CH50 at all visits specified. Antiphospholipid antibodies will be evaluated at baseline only.
- i INR, APTT, and fibrinogen at all visits specified. Lupus anticoagulant panel will be evaluated at baseline only.
- j When needed for SLEDAI-2K assessments and scoring, a Coombs test could be performed locally to confirm hemolytic anemia, and ultrasound or other evaluation (e.g., chest radiograph, echocardiogram) could be performed as needed to confirm pleuritis (pericarditis or pneumonitis).
- k Week 1, Day 1, predose and 4 hours post-dose; Week 5, Day 29 pre-dose only.
- l All AEs must be recorded on the patient’s electronic case report form (eCRF), starting at the time of informed consent and continuing through after 12 weeks post last dose. Prior medications will be collected at the screening visit. Concomitant medications will be collected at each visit.

Abbreviations: AEs = adverse events; ANA = antinuclear antibody; APTT = activated partial thromboplastin time; C3/C4 = complement 3 and 4; CH50 = 50% hemolytic complement; D = day; DNA = deoxyribonucleic acid; ECG = electrocardiogram; EOS = End of Study; FCBP = females of child bearing potential; HAQ-

DI = Health Assessment Questionnaire-Disability Index; hr = hour; Immunoglobulin (Ig); INR = international normalized ratio; min = minutes; PGA = Physician Global Assessment of Disease Activity; PK = pharmacokinetic; PtGA = Patient Global Assessment of Disease Activity; PtGP = Patient Global Assessment of Pain; SLE = Systemic Lupus Erythematosus (includes lupus nephritis); SLEDAI-2K = Systemic Lupus Erythematosus Disease Activity Index 2000; SJC-28 = Swollen 28-Joint Count; TJC-28 = Tender 28-Joint Count; SLICC = Systemic Lupus International Collaborating Clinics; TB = tuberculosis; UPCR = Urine Protein to Creatinine Ratio.

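### The plan does not require a Week 25 UPCR, the primary outcome, from Phase 2 patients who stop study drug for a reason other than an AE and still consent

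*Combined protocol and SAP*

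**What the plan says.** - **Primary endpoint.** Section 11.1.2: "The number of patients with a 50% reduction in UPCR after 24 weeks of treatment when compared to baseline".
- **When UPCR is measured.** Section 8.2.6.5: "24-hour urine samples will be collected at Weeks 1, 5, 9, 13, 17, 21, 25, 29, 33, and 37", with a first-morning spot sample at the same visits. Appendix B places Week 25 at Day 169 ±1 day.
- **Stopping because of an AE.** Section 7.1.4 (Missed Doses) has a sentence that begins "If study medication is permanently discontinued due to an AE, standard therapy and planned assessments" and goes on to say that both should continue for the period set by the protocol. The same subsection requires permanent discontinuation when dosing cannot resume within 2 weeks of the first missed dose, or when more than 6 Phase 2 doses are missed for whatever cause. Doses missed under the Study Stopping Rules are excepted. It attaches no follow-up rule to discontinuations that are not due to an AE.
- **Stopping treatment in general.** Section 9.2 is headed as withdrawal from the study but lists reasons for stopping study drug. These include non-compliance, non-permitted therapy, investigator or sponsor request, and several AE reasons. It then says: "Patients withdrawing from the study treatment will be encouraged to complete the Early Withdrawal Visit within 7 days and return for an EOS Visit". The EOS Visit is timed "approximately 12 weeks after receipt of their last dose to complete the final evaluations according to this protocol, particularly safety evaluations". The section also states a general aim of recording data as for completers.
- **Early Withdrawal Visit content.** The laboratory item in Section 9.3 reads "Collect samples for hematology, clinical chemistry, and urinalysis tests". Neither 24-hour urine nor UPCR is listed. The EOS/ETV column of Appendix B does appear to carry the 24-hour urine test.
- **Analysis.** Section 11.3.6: "Patients who are withdrawn prematurely from investigational product and/or the study will be included in all analyses regardless of the duration of treatment". It allows no imputation unless otherwise specified. Section 11.3.5 summarises binary endpoints by the number of patients observed.

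**The concern.** The analysis section expects patients who come off drug to contribute to every analysis, but the visit rules do not ask most of them for the one measurement that defines the primary outcome. The only sentence that continues the schedule after drug is stopped is conditional on an AE. Everyone else is offered two visits, one timed from withdrawal and one from the last dose, while the endpoint is timed from Day 1.

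The missing values would probably be informative. Patients stopped for non-compliance or for taking non-permitted therapy are plausibly non-responders. If they drop out of the denominator, the observed response rate rises. Each patient is 5% of the planned 20.

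There is also an inconsistency. An AE-related stop falls under both Section 7.1.4 (planned assessments continue) and Section 9.2 (Early Withdrawal Visit and EOS Visit), and the two give different follow-up.

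**Working it through.** The plan states no alpha, sidedness, power or dropout rate, so it offers no figure of its own to reproduce. Two checks were made.

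**1. Where the EOS Visit falls relative to Week 25**

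Inputs: "KZR-616 dose administration on day one of each week from Week 1 up to Week 24" (Appendix B, footnote f); EOS about 12 weeks, or 84 days, after the last dose (Section 9.2); Week 25 on Day 169 (Appendix B), which is 24 × 7 = 168 days after Day 1.

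Formulas: last-dose day = 1 + 7 × (week − 1); EOS day = last-dose day + 84; gap = EOS day − 169.

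| Last dose (week) | Last-dose day | EOS day | Gap from Day 169 |
|---|---|---|---|
| 1 | 1 | 85 | −84 |
| 8 | 50 | 134 | −35 |
| 12 | 78 | 162 | −7 |
| 13 | 85 | 169 | 0 |
| 14 | 92 | 176 | +7 |
| 18 | 120 | 204 | +35 |
| 20 | 134 | 218 | +49 |
| 23 | 155 | 239 | +70 |

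Across the 23 possible early last-dose weeks, the EOS Visit lands on Day 169 in one (Week 13) and within 7 days of it in three (Weeks 12 to 14).

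Replacement matters here. Sections 5.1 and 9.2 allow a Phase 2 patient who withdraws before the Week 14 injection to be replaced, so many of the early stops can be made up in number. A patient whose last dose was at Weeks 14 to 23 cannot be replaced, and for these the EOS Visit is 7 to 70 days late.

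The Early Withdrawal Visit follows the withdrawal date. It can fall near Week 25 for a late stop: after a last dose on Day 155, withdrawal on Day 162 gives a window to 162 + 7 = Day 169. Whether UPCR would be taken then depends on whether Section 9.3 or the Appendix B EOS/ETV column is followed.

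**2. What the loss can do to the primary test**

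Inputs: planned n = 20 (Section 5.1); null response rate of at most 20% and an exact binomial test (Section 11.3.5). Assumptions: one-sided testing at 0.05, with 0.025 shown for range; the number of patients lost; and that the lost patients are non-responders who leave the denominator.

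Formula: p = Σ from k = r to n of C(n, k) × 0.2^k × 0.8^(n − k).

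| Responders / measured | p |
|---|---|
| 7/20 | 0.0867 |
| 7/19 | 0.0676 |
| 7/18 | 0.0513 |
| 7/17 | 0.0377 |
| 8/20 | 0.0321 |
| 8/19 | 0.0233 |

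At 0.05, three lost non-responders turn 7 responders from non-significant to significant. At 0.025, one lost non-responder does the same for 8 responders.

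**The case against.** A reader might infer that these patients leave the visit schedule and that their Week 25 UPCR is never collected. The documents do not go that far. Section 9.2 encourages two visits without cancelling the others, and it aims to record data as for completers. Section 7.1.4 says that assessments continue after an AE stop; it does not say that they end for other stops. A last dose at Week 13 puts the EOS Visit on Day 169 itself. Section 9.2 also covers AE reasons, so it is not a separate path for non-AE stops. What stands is that the Week 25 measurement is not required.

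A reader might also compare 8/20 with 7/20 and conclude that one lost outcome reverses the result. That needs the lost patient to be a responder, which runs against the expectation that these patients are mostly non-responders, and it needs a threshold that the plan does not state.

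The affected group may be small. Some forced discontinuations will follow failed dosing criteria that are themselves AEs and so fall under Section 7.1.4. Early stops can be replaced, although replacement does not settle who is in the denominator. No dropout rate is given.

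Finally, the endpoint is binary, so a non-responder rule would give every patient an outcome. Section 11.3.5 refers to the SAP for details, and Section 11.3.1 gives the SAP precedence. No separate SAP text was available for this review, so such a rule cannot be excluded. It would settle the denominator but would not supply the measurement.

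**Conclusion.** The point holds as a gap in required data collection. For a Phase 2 patient who stops drug for a non-AE reason and still consents, no section requires the Week 25 UPCR. The EOS Visit that is offered falls on Day 169 for one of 23 last-dose weeks and within 7 days for three, and it is 7 to 70 days late after last doses at Weeks 14 to 23. Sections 7.1.4 and 9.2 conflict for AE stops, and Section 9.3 appears to conflict with Appendix B on the 24-hour urine; the extracted table is imperfect on that last point.

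The effect on the test (7/20, p = 0.087, against 7/17, p = 0.038) rests on an assumed one-sided 0.05, an assumed three losses, those losses being non-responders, and a denominator of measured patients only. It shows what could happen and does not forecast it.

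This should be fixed, as an inexpensive improvement. A stronger rating is not supported for an open-label, single-arm phase of 20 patients that Section 11.4 says is not powered for hypothesis testing.

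**What to change.** 1. In Sections 7.1.4 and 9.2, distinguish stopping study drug from withdrawing consent for the study. This concerns data collection only; the rules on when drug is stopped are untouched.
2. State that patients who stop drug for any reason and still consent remain on the Appendix B visits counted from Day 1. At minimum this means the Week 25 24-hour and spot UPCR, creatinine/eGFR and the medication record. One rule for all reasons also removes the overlap for AE stops.
3. Reconcile the Section 9.3 list with the Appendix B EOS/ETV column on 24-hour urine and UPCR.

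The cost is protocol wording and a few collections that are already scheduled, with a small extra visit burden for the patients who stop drug. The change cannot recover outcomes after withdrawal of consent or loss to follow-up.

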9.3 Early Withdrawal (or Discontinuation) Visit

The Early Withdrawal Visit will take place within 7 days after withdrawal. The following procedures will be performed at the Early Withdrawal Visit:

- Record any AEs that have occurred since the last visit and any changes in concomitant medication
- Record vital signs
- Record any changes from baseline in physical examination as AEs
- Collect samples for hematology, clinical chemistry, and urinalysis tests

9.4 Study Termination

The sponsor has the right to terminate the study at any time in case of SAEs or if special circumstances concerning the study drug or the company itself occur that makes further treatment of patients impossible. In this event, the investigator(s) will be informed of the reason for study termination.

10 ADVERSE EVENTS AND SERIOUS ADVERSE EVENTS

10.1 Adverse Event Reporting

10.1.1 Definitions

An AE is defined as any untoward medical occurrence in a clinical study patient administered a medicinal product, which does not necessarily have a causal relationship with this treatment. An AE can therefore be any unfavorable and unintended sign (including an abnormal laboratory finding), symptom, or disease temporally associated with the use of a medicinal (investigational) product, whether or not it is related to the medicinal (investigational) product. This includes an exacerbation of pre-existing conditions or events, intercurrent illnesses, drug interaction or the significant worsening of the indication under investigation that is not recorded elsewhere in the eCRF under specific efficacy assessments. Anticipated fluctuations of pre-existing conditions, including the disease under study, that do not represent a clinically significant exacerbation or worsening need not be considered AEs.

It is the responsibility of the investigator to document all AEs that occur during the study. AEs will be elicited by asking the patient a nonleading question, for example, "Have you experienced any new or changed symptoms since we last asked/since your last visit?" AEs should be reported on the appropriate page of the eCRF.

10.1.2 Assessment of Severity

Severity of AEs will be graded according to NCI-CTCAE version 4.03. If there is a change in severity of an AE, it must be recorded as a separate event.

10.1.3 Assessment of Causality

AEs will be deemed related to study medication unless clearly unrelated to study medication.

The principal investigator will assess the causal relationship. One of the following categories should be selected based on medical judgment, considering the definitions below and all contributing factors.

Related	A clinical event, including laboratory test abnormality, occurs in a plausible time relationship to treatment administration and which concurrent disease or other drugs or chemicals cannot explain. The response to withdrawal of the treatment (dechallenge ^a) should be clinically plausible. The event must be definitive pharmacologically or phenomenologically, using a satisfactory rechallenge ^b procedure if necessary.
Unrelated	A clinical event, including laboratory test abnormality, with little or no temporal relationship with treatment administration. May have negative dechallenge and rechallenge information. Typically explained by extraneous factors (e.g., concomitant disease, environmental factors, or other drugs or chemicals).

^a Dechallenge: Upon discontinuation of a drug suspected of causing an AE, the symptoms of the AE disappear partially or completely, within a reasonable time from drug discontinuation, (positive dechallenge), or the symptoms continue despite withdrawal of the drug (negative dechallenge). Note that there are exceptions when an AE does not disappear upon discontinuation of the drug, yet drug-relatedness clearly exists (for example, as in bone marrow suppression, fixed drug eruptions, or tardive dyskinesia).

^b Rechallenge: Upon re-administration of a drug suspected of causing an AE in a specific patient in the past, the AE recurs upon exposure (positive rechallenge), or the AE does not recur, (negative rechallenge).

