4.1.1.1 Dose-Limiting Toxicities

A DLT is defined as any Grade 3 or higher study drug-related AE, according to National Cancer Institute Common Terminology Criteria for Adverse Events (NCI-CTCAE), Version 4.03, that occurs during the 4-week DLT evaluation period, with the following exceptions:

- Asymptomatic Grade 3 anemia, neutropenia, or thrombocytopenia returning to baseline or Grade ≤ 2 within 7 days without transfusion, growth factor support, or other active therapeutic intervention
- Grade 3 study drug administration-related reactions (e.g., systemic drug reaction), fatigue, anorexia, chills, nausea, diarrhea or vomiting lasting < 1 day

-
- Asymptomatic, isolated Grade 3 or higher changes in alkaline phosphatase, creatine phosphokinase, gamma-glutamyl transferase, lipase, or lymphocyte count

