4.1.1.2 Dose Escalation Plan

For each dose level, at least 6 patients may be enrolled to assure the availability of at least 4 DLT-evaluable patients. Dose escalation guidelines are as follows:

- Each cohort within a dose level will include 1 sentinel patient who will receive KZR-616 at a selected dose on Day 1/Week 1
- If the sentinel patient does not experience a DLT, as defined below, within 48 hours and based on the clinical judgement of the investigator and medical monitor, the remaining patients in the cohort will be dosed
- If a DLT is experienced in the sentinel patient within 48 hours of injection, a second sentinel patient may be dosed with KZR-616 following a safety review by the DMC. If no DLT is observed after 48 hours in the second sentinel patient, the remainder of the cohort may be enrolled
- If 0 or 1 of 6, 0 or 1 of 5, or 0 of 4 patients (20% or less) in a cohort experience a DLT, the next dose level will be opened for enrollment after DMC review as below
- If 1 of 4 (25%) patients in a cohort, or 2 or more of 5 or 6 patients in a cohort experience a DLT, the maximum tolerated dose will have been exceeded and dose escalation will not continue

To evaluate tolerability, a minimum of 4 patients should receive KZR-616 at a specified dose level for at least 4 weeks prior to any decision by the DMC to dose escalate.

Patients who discontinue treatment prior to Week 5 will be considered DLT non-evaluable, unless they experience a DLT prior to Week 5. The DLT non-evaluable patients may be replaced until the necessary number of evaluable patients is achieved per dose level.

Escalation is planned to continue in 15 mg increments of KZR-616. Planned dose levels of KZR-616 to be explored are described in [Table 2](#) below. Other dose escalation increments may be proposed by the DMC based upon emerging safety, PK, PD, and/or efficacy data. Similarly, emerging data may prompt the DMC to recommend a different DLT evaluation period, or alteration of the dosing interval or duration. During the dose escalation period, and based on safety evaluation in patients, the DMC may also recommend that patients in subsequent dose cohorts receive prophylactic treatment (e.g., pulse corticosteroid and/or antihistamine) prior to initial doses to prevent AEs and/or intra-patient dose escalation to be employed with an initial tolerizing dose of 30 mg.

Table 2: KZR-616 Dose Levels

Dose of KZR-616 (mg)
45 mg
60 mg
75 mg

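### Section 10.1.3 sets two conflicting tests for a drug-related AE and does not say which governs, so a plausibly timed event with another possible cause has no settled label

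*Combined protocol and SAP*

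**What the plan says.** Section 10.1.3 starts with a rule for all adverse events: "AEs will be deemed related to study medication unless clearly unrelated to study medication". The investigator is then told: "One of the following categories should be selected based on medical judgment, considering the definitions below and all contributing factors". There are two categories.

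- *Related* needs plausible timing and an event "which concurrent disease or other drugs or chemicals cannot explain". It asks for a plausible response to withdrawal and adds: "The event must be definitive pharmacologically or phenomenologically, using a satisfactory rechallenge". Rechallenge is qualified as being used only where needed.
- *Unrelated* describes an event "with little or no temporal relationship with treatment administration". An outside explanation is given as typical of this category, not as sufficient for it.

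Footnote a softens the withdrawal condition: "Note that there are exceptions when an AE does not disappear upon discontinuation of the drug, yet drug-relatedness clearly exists".

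The label is used elsewhere. Section 4.1.1.1 says: "A DLT is defined as any Grade 3 or higher study drug-related AE", with listed exceptions and a 4-week window. Section 4.1.1.2 ends escalation under this condition: "If 1 of 4 (25%) patients in a cohort, or 2 or more of 5 or 6 patients in a cohort experience a DLT".

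**The concern.** The default and the *Related* row put the burden of proof on opposite sides. Under the default, doubt leads to related. Under the row, doubt about another cause rules related out. Nothing in 10.1.3 ranks one above the other.

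The events affected are foreseeable. Section 4.1.2 requires every Phase 2 patient to be on at least one immunosuppressive agent, and the synopsis requires a stable SLE regimen in Phase 1b (Section 2.5.3 is looser, saying that patients may be on therapy). A cytopenia or an infection after dosing could often be put down to a background drug. Section 10.4 narrows the group by keeping non-serious SLE manifestations out of AE recording, but it does not cover events that background drugs might explain.

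If two sites follow different sentences, the same Grade 3 event could be a DLT at one and not at the other.

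**Working it through.** **Step 1. Apply each text to the middle case:** plausible timing, with another disease or drug that could explain the event.

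| Text in 10.1.3 | Condition | Middle case |
|---|---|---|
| Opening default | related unless clearly unrelated | related, since it is not clearly unrelated |
| *Related* row | no other explanation possible; event definitive | not met |
| *Unrelated* row | little or no temporal link | not met |
| Footnote a | relaxes the withdrawal condition only | does not touch the alternative-cause condition |

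One text assigns the event to a category whose own definition excludes it.

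**Step 2. Trace where the label is used.**

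- It affects the DLT definition (4.1.1.1) and the escalation count (4.1.1.2).
- It affects the individual stopping rule for events meeting DLT criteria, in both phases (9.1).
- It affects eligibility for dose reduction, which also needs investigator discretion and approval (7.1.4).
- It affects the SAE-form route from 30 days after the last dose to the end of the 12-week follow-up (10.2.2).
- It affects the AE tables by investigator causality (11.3.1).
- It does not affect the safety endpoints (synopsis, 11.1.1, 11.1.2), collection of all AEs to 12 weeks after the last dose with seriousness recorded (10.1.5, 10.1.6), SAE reporting up to 30 days (10.2.2), or the pre-dose criterion on AE grade (7.1.1).

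**Step 3. Find the margin in the escalation rule.** Inputs are from 4.1.1.2: escalate at 0 of 4, or at 0 or 1 of 5 or 6; otherwise stop. I read the 4-patient stop as 1 or more. Take a patient who is already DLT-evaluable and has no other DLT, with a non-exempt Grade 3 or higher event inside the 4-week window. Relabelling the event as related moves the cohort from k/n to (k+1)/n.

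| n | Single steps possible | Step that changes the decision | Proportion |
|---|---|---|---|
| 4 | 4 | 0/4 to 1/4 | 0% to 25% |
| 5 | 5 | 1/5 to 2/5 | 20% to 40% |
| 6 | 6 | 1/6 to 2/6 | 16.7% to 33.3% |

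Every other single step leaves the decision as it was, for example 0/6 to 1/6 or 2/6 to 3/6.

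**Step 4. Allow for early stoppers.** Under 4.1.1.2 a patient who stops before Week 5 is not evaluable unless there was a DLT. Relabelling then adds to both parts of the fraction, so k/n becomes (k+1)/(n+1).

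- 0/4 becomes 1/5 (20%): still escalate.
- 0/5 becomes 1/6 (16.7%): still escalate.
- 1/5 becomes 2/6 (33.3%): stop.
- 1/6 becomes 2/7 (28.6%): the rule gives no count for 7.

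No event rate is assumed in any step.

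**The case against.** The strongest reply is that 10.1.3 works as one rule. The default is mandatory and covers every AE, while the rows only guide medical judgment. An event that is not clearly unrelated is therefore related, and each AE already receives one of two labels. This is the better reading of the section. It does not remove the conflict: the text never says that the default prevails, the next sentence sends the investigator to the rows, and the *Related* definition is false for the events that the default places there. A site could also lean on the mention of outside factors in the *Unrelated* row.

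Safeguards also limit the effect. The DMC reviews safety data before escalation (4.1.1.2, 10.7). Dosing is withheld for non-injection-site AEs above Grade 2 whatever their cause (7.1.1). The study stopping rules in 9.1 turn on obvious alternative etiology, not on relatedness. These stand as protections for patients, but none says which definition sets the DLT count or the causality tables. The DMC charter is a separate document, so whether it contains an adjudication step is not known.

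A reader might infer that late SAEs labelled unrelated are lost. They are not: they are still collected as AEs and summarised, and only the SAE-form route depends on the label. A reader might also infer that the primary or secondary safety endpoints are compromised. Those are defined by incidence, nature and severity, together with other safety findings in 11.1.1, and not by causality.

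**Conclusion.** The inconsistency is real and should be corrected. It is a conflict between two stated rules, not a missing detail. An investigator who applies the *Related* row as written would leave middle-case Grade 3 or higher events out of the DLT count, the DLT-based individual stop and the related-AE tables. One who applies the default would include them.

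The size is bounded in form but not in frequency. For an evaluable patient, one relabelling matters at a single step per cohort size, and for an early stopper the effect differs as shown. The documents give no rate of events with more than one possible cause, so no probability of a changed decision can be offered.

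Three further inferences are not supported. That sites have in fact labelled events differently is a possibility, not something the documents show. Nor does the conflict show that any escalation decision was wrong. The 60 mg level for Phase 2 is already fixed in 4.1.2 and 7.1, and nothing here shows that it was wrongly chosen. What remains exposed is Phase 1b DLT reporting, any remaining escalation and Phase 2 safety classification.

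The conclusion rests on 10.1.3 as written. Section 11.3.1 gives the SAP precedence over the protocol, and no causality rule from a SAP appears in the text reviewed.

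**What to change.** Reconcile 10.1.3. State which text governs, and reword both rows to match it so that every AE falls in exactly one category. One way is to follow the protocol's own mandatory default: *Unrelated* would cover events that are clearly unrelated, and *Related* all others. State that this single definition applies wherever the protocol uses relatedness, including 4.1.1.1, 7.1.4, 9.1, 10.2.2 and 11.3.1, and carry it into the eCRF guidance.

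Leave the DLT, stopping, dosing and dose-reduction rules unchanged. Retrospective re-adjudication is not required.

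The cost is a wording amendment, updated eCRF guidance and site retraining. If the default is followed, some events may be over-attributed to study drug.
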